24.0 Economic Burden to Participants

24.1 Potential costs

Since data collection will be done remotely, there are few potential costs associated with participation.

25.0 Resources Available

 Will the research be conducted 	✓ YES (complete 25.1)
outside School of Medicine and	☐ NO (remove text below, but retain this
Public Health or UW Hospitals	section)
and Clinics (e.g. the researcher	section)
does not have an SMPH	
research feasibility attestation	
for this study)?	

25.1 Resources available to conduct the research

The Center for Healthy Minds has ample experience running large-scale, longitudinal studies. As most studies have moved to remote data collection in the past year (IRB protocols: 2020-0533, 2020-1454, and 2019-0893), we have been successful at recruiting a large number of participants with high retention rates.

Data collection for this study will be completed remotely over approximately 3 years.

We will inform participants that they should contact their healthcare provider if any concerns arise when answering survey questions. A therapeutic resource list will be provided to all participants upon completion of the study.

Study staff will meet on a regular basis to discuss study design, implementation, processing, and analyses. We will discuss task assignments and study updates at these meetings.

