13.2 Schedule of study procedures

13.2 Schedule of study proce	dures			4-W Interv		
Study Procedure/Activity	Web Screen	Phone/ Zoom Call	T1	T2-T4	T5	Т6
Consent via Information Sheet	X					
Screening Questions	X					
Review Eligibility	X					
Informed Consent Process for		X				
Main Study						
Payment Information Survey		X				
Payment Information Update						X
Survey						
Intervention (i.e., Healthy				X^1	X^1	
Minds Program)						
Behavioral Pattern Separation			X		X	X
Task						
Attention Check Items			X		X	X
Behavioral Risk Factor			X			
Surveillance System (BRFSS)						
Adverse Childhood						
Experiences (ACE) Module						
Demographics			X			
Demographics & Meditation			X			
Experience						
Determinants of Meditation			X			
Practice Inventory-Revised						
(DMPI-R)						
Digital Working Alliance				X^1	\mathbf{X}^1	
Inventory (DWAI)						
Feedback Survey			X	X	X X	X
Five Facet Mindfulness			X		X	X
Questionnaire (FFMQ),						
Awareness Subscale						
Flourishing Measure			X		X	X
Global Physical Activity			X		X	X
Questionnaire (GPAQ)						

Healthy Minds Index		X		X	X
(HMIndex)					
Mainz Inventory of		X		X	X
Microstressors (MIMIS)					
Marlowe-Crowne Social		X			
Desirability Scale (MCSDS)					
Mindfulness-Based Program -				X^1	
Meditation-Related Adverse					
Effects Scale (MBP-MRAES)					
Mindfulness Adherence			X^1	X^1	X^1
Questionnaire (MAQ)					
NIH Toolbox Loneliness		X		X	X
Pre- & Post-Practice Items			X	X	
PROMIS Item Bank -	X	X	X	X	X
Emotional Distress - Anxiety					
(Computer Adaptive Version)					
PROMIS Item Bank -	X	X	X	X	X
Emotional Distress -					
Depression (Computer					
Adaptive Version)					
PROMIS Item Bank -		X	X	X	X
Emotional Distress - Sleep					
Disturbance (Computer					
Adaptive Version)					
Perceived Stress Scale (PSS)		X	X	X	X
PTSD Checklist (PCL-5)		X		X	X
Location Tracking with		X^2	X^2	X^2	X^2
Passive GPS ⁴					
Debriefing Form					X

¹HMP group only

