13.3 Research procedures

For this study, participants will complete tasks remotely, including online surveys and computerized tasks, the Healthy Minds Program (if assigned to the HMP group), and location tracking using a GPS app downloaded to participants' phones. We plan to enroll 150 participants.

Location Tracking: Throughout the study we will track participant location using GPS smartphone technology, which allows smartphones to automatically and passively (no participant input needed) capture information about the participant's activity (e.g., if the person is walking, remaining stationary, or moving at a rapid speed). After providing informed consent, participants will be oriented to the mobile phone application and will be instructed on downloading, installing, and optimizing the smartphone application required for participation. Real-world data collection will occur for approximately 4-5 months, from the time of consent until the 3-Month Follow-Up. Participants will be asked to keep their phone with them and powered on as much as possible during the study. The smartphone application will use an activity classifier program to determine if the user is remaining stationary, walking, or driving based on how quickly Wi-Fi and GPS signals change and on the strength of motion detected by the accelerometer. During the

²Location Tracking collected continuously throughout the study

3-Month Follow-Up (or if a participant discontinues the study), we will instruct participants on disabling the location tracking app.

Timepoint 1 - Pre-Intervention Activities: Participants will complete pre-intervention online surveys and tasks remotely using the REDCap system (see section **13.2 Schedule of study procedures** for measures that will be administered). Timepoint 1 will take 30 to 45 minutes. Survey and task completion will be self-paced, but we will ask participants to complete these activities within one week of receiving the REDCap link. Participants who do not complete the Timepoint 1 activities within one week may be unenrolled from the study.

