22.0 Risks to Participants

22.1 Risks, discomforts, hazards, or inconveniences

Risk of emotional responses:

Study surveys include questions about mental health that could affect a participant's mood or make them feel embarrassed. Emotional upset due to study participation is a potential but unlikely risk. In our experience from previous studies, it is rare for a participant to find self-report questionnaires to be extremely upsetting.

Risk of location tracking:

GPS location data collected from participants' smartphones could be used to see specific locations that participants have visited and whether participants may have engaged in activities or visited places that are potentially stigmatizing or embarrassing.

Risk of confidentiality breach:

There is a slight risk of breach of confidentiality, which could result in legal implications or stigmatization. There is a chance that concerns about safety (e.g., self harm, possible child abuse) will be discovered during the course of the study, and that these discoveries could require mandatory reporting and place subjects at possible legal risk. There is the risk that information, such as health information or GPS location information, could become known to subjects, doctors, or others. If this happens it may lead to loss of insurance, difficulty obtaining insurance, an increase in premiums, job loss, reduced employability, and harmful psychological effects on the subject.

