22.6 Minimizing risks

Minimizing risk of emotional responses:

We will inform participants in the consent form and in survey instructions that some questions may ask about sensitive topics and that they may skip any items that they are not comfortable answering, except for certain required items (e.g., the PSS is required because it is a primary study measure). As stated in the consent form, participants are free to discontinue at any point during the experiment.

If a participant reveals suicidal ideation, self-harm, or intent to harm others, study staff will consult with clinical research personnel. A clinician will contact the participant by phone to assess intent, the level of risk, and provide referrals as needed. In the circumstance that an individual indicates that self-harm or harm to others is imminent, 911 will be called. All interactions regarding suicide risk and referral will be carefully documented and closely tracked by the clinical research personnel. A formal incident report will be filed with the IRB in cases in which a clinician notifies authorities. All participants will be provided with therapeutic resources regardless of their responses.

Minimizing risk of location tracking:

We will inform participants in the consent form about how we will use and protect location data. The FollowMee app will not collect any identifying information. Location data will only be associated with a non-identifiable device ID and subject ID. Data will be stored on secure password-protected servers. Study staff will not view real-time GPS locations, other than to confirm that the FollowMee app is functioning correctly. Data will be encrypted during download, and security measures for the Center for Healthy Minds network will provide protection against data breach. After the data are downloaded, our staff will protect participant confidentiality by not viewing or analyzing the minute-by-minute data, other than for the purpose of conducting quality control checks of these data. When reviewing these data, staff will view lists of latitude/longitude coordinates, and will make no effort to link these coordinates to specific places that could reveal embarrassing, stigmatizing, or illicit information. Data analysis will focus on extracted summary measures across a given day; for example, total distance traveled, number of distinct locations visited, and diversity of locations visited (or "roaming entropy"; see Heller et al., 2020).

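### The only stated delivery time for the therapeutic resource list is study completion, about 17 weeks after the first trauma questions, and the withdrawal steps do not mention it

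*Combined protocol and SAP*

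**What the plan says.** Two places in the combined protocol and SAP promise the material to everyone. Section 22.6, under the measures against emotional responses, says "All participants will be provided with therapeutic resources regardless of their responses", without a time. Section 25.1 supplies one: "A therapeutic resource list will be provided to all participants upon completion of the study".

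The schedule in 13.2 places the ACE module at T1 only and the PCL-5 at T1, T5 and T6. The "Debriefing Form" appears at T6 only.

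Sections 15.2 and 15.3 number the steps for withdrawal by the study team (five) and by the participant (six). Both end by telling the leaver that the meditation app is free to use. Neither mentions the resource list. Section 13.3 also allows removal at the start: "Participants who do not complete the Timepoint 1 activities within one week may be unenrolled from the study".

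Section 22.1 rates the risk: "Emotional upset due to study participation is a potential but unlikely risk".

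**The concern.** A resource list meant to limit upset from survey questions is most useful when it arrives with those questions. At its one stated time, it arrives after all of them. The ACE module and the first PCL-5 are completed remotely, with no staff member present.

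The second difficulty is reach. Delivery at completion does not by itself serve people who never complete. Staff handling a withdrawal have a written sequence to follow, and nothing in it prompts them to send the list. The promise in 22.6 and 25.1 covers all participants, but the only stated delivery point covers those who reach the end.

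What is at stake is a modest participant protection. No endpoint, estimate or test depends on it.

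**Working it through.** **1. The plan's own duration.** Section 12.1 gives individual participation as approximately 4-5 months. One month is 365.25 / 12 / 7 = 4.348 weeks, so this is 4 × 4.348 = 17.4 to 5 × 4.348 = 21.7 weeks.

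**2. T1 to T6.** Inputs from 13.3: T2-T5 fall in the weeks of the 4-week program, and T6 comes about three months after T5.
- T1 to T5: about 4 weeks.
- T5 to T6: 3 × 4.348 = 13.0 weeks.
- T1 to T6: 4 + 13.0 = 17.0 weeks, or 17.0 / 4.348 = 3.9 months.
- Taking three months as 12 weeks: 4 + 12 = 16 weeks.
- Adding the one-week T1 window (13.3) and an assumed one-week window at T6: 17.0 + 2 = 19.0 weeks, or 4.4 months.

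The interval is about 17 weeks, range 16 to 19, which agrees with the stated 4-5 months. Completion is read here as the participant's own T6. If it meant the end of the whole trial, the delay would be longer.

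**3. Where the questions fall.**

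| Item | Timepoints | Approximate time before the stated delivery at T6 |
|---|---|---|
| ACE module | T1 | 17 weeks |
| PCL-5, first | T1 | 17 weeks |
| PCL-5, second | T5 | 13 weeks |
| PCL-5, third | T6 | 0 |
| Debriefing Form | T6 | 0 |

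The content of the Debriefing Form is not shown. Since it is scheduled at T6 only, it could not bring the list forward.

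**4. Are the withdrawal steps complete?** No. Section 13.3 adds a discontinuation step that is in neither 15.2 nor 15.3: during the "3-Month Follow-Up (or if a participant discontinues the study), we will instruct participants on disabling the location tracking app". Silence in 15.2 and 15.3 therefore does not prove that leavers go without the list. It shows only that no written step delivers it to them.

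**5. Supports available before completion.**
- Items may be skipped, apart from certain required ones such as the perceived stress scale (17.3, 22.6).
- Participants are invited to tell staff about concerns at any time (17.3).
- The consent call makes sure they know whom to contact (8.1).
- Section 25.1 adds: "We will inform participants that they should contact their healthcare provider if any concerns arise when answering survey questions".
- If suicidal ideation, self-harm or intent to harm others is revealed, 22.6 provides: "A clinician will contact the participant by phone to assess intent, the level of risk, and provide referrals as needed".

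Below the threshold for the clinician call, a participant still has the first four.

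**The case against.** The strongest reply is that this is unspecified timing and that nothing shows a withheld safeguard. Section 22.6 is the operative risk section and sets no late date. The consent form and survey instructions, where the plan puts its warnings about sensitive questions, are not in the review copy and may already carry the list. That is a fair limit: earlier provision cannot be excluded. It does not alter the one time that is written down, and the fix allows for it.

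A second reply is that participants have several other supports and that upset is rated unlikely in a healthy sample. This stands, and it is why the expected benefit is small.

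A third is that sensitive questions begin before T1, since the eligibility survey asks about psychiatric symptoms (8.2, 17.2). A T1 mailing does not reach that stage. Under 4.3, however, people count as enrolled only after consent, so the commitment to all participants starts later than the screener.

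A reader might infer that 22.6 and 25.1 contradict each other, or that people who withdraw are denied the list. The documents support neither. One passage has no time and the other has a late one, which is compatible. The withdrawal steps are not exhaustive.

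**Conclusion.** The point holds as a cheap improvement in participant safety. The stated delivery time is about 17 weeks after the ACE module and first PCL-5, and no withdrawal step covers the list, so as written early leavers may not receive it. This rests on reading completion as the participant's T6 and on the visible text alone.

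Two larger-looking figures should not be read as its size:
- A reader might take the 10% dropout in 20.2, 0.10 × 150 = 15, as the number who would go without the list. That 10% is a sample-size assumption. It does not separate withdrawal from silent loss or say when people leave, and some leavers may receive the list anyway.
- A reader might count ACE and PCL-5 administrations before T6, (150 + 300) / (150 + 450) = 75%, as the share left unprotected. That share only reflects the visit schedule and the choice of two instruments. It does not measure distress, and other supports are in place throughout.

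The documents give no rate of distress, so the number of people who would benefit cannot be estimated.

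**What to change.** - In 25.1, replace the completion timing with: *with the Timepoint 1 survey link, and again at completion or withdrawal*.
- In 15.2 and 15.3, add a numbered step: *provide the therapeutic resource list*.
- If the consent form or survey instructions already carry the list, say so in 25.1 and add only the withdrawal steps.

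The T1 mailing is the part that reaches people who stop responding or are unenrolled at T1. Anyone still in follow-up when the change is made can be sent the list once.

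The cost is three short text edits and the trivial effort of attaching a document the study already plans to provide. The one downside for the trial is a possible slight increase in care-seeking before T5, which could affect the perceived stress comparison. Its size cannot be estimated from the documents. Because T1 precedes randomization (13.1), both groups would be sent the list on the same terms, so any effect on the contrast would have to come from different use of it. Record the date of the change, since earlier and later enrollees would receive the list at different times. No endpoint or analysis changes.

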26.0 Multi-Site Research

N/A

28.0 Appendices

N/A
